About 1 in 7 U.S. children < 18 years are classified as children with special health care needs (CSHCN) and require health services beyond routine care. Among CSHCN is a vulnerable subgroup, known as children with medical complexity (CMC), who has life-threatening, complex, multisystem conditions, frequent emergency department (ED) and hospital admissions, and account for 1/3 of pediatric health care expenditures. CMC often have severe neurological impairment, marked intellectual and physical disabilities, and depend on technology to sustain life. CMC prevalence among hospital admissions is increasing nationally, mainly due to improved survival of children with conditions previously incompatible with life. Once discharged, CMC continue to experience frequent acute deteriorations of their health status often for potentially avoidable causes and/or technology malfunctions that lead to recurrent ED/hospital admissions. Overall, CMC have significant ongoing care needs and require substantial care coordination and constant caregiver attention. Long-term caregiving can stress family caregivers and impose a significant caregiver burden, leading to burnout, which may affect caregivers' health and thereby ability to provide care to CMC, setting up a vicious cycle of negative outcomes. To reduce the risk of acute deteriorations of a chronic condition, self-management is recommended. Better support for self-management improves outcomes. Existing selfmanagement support interventions focus primarily on non-complex, single system conditions. No intervention exist to address the variable, multisystem diagnoses of CMC or to target caregiver burden. Despite variable diagnoses, CMC are often admitted to the ED/hospital for common, crosscutting symptoms. Such similarity presents an opportunity for innovative self-management interventions, appropriate to CMC. We propose to develop and test the impact of a mobile health application to engage caregivers in self-management of CMC (MyChild^{CMC}), targeting crosscutting symptoms coupled with ongoing monitoring of caregiving burden to promote timely decision-making.

7/9/2021

IRB_00088596

B_00088596 Created: 12/9/2015 12:01 PM : [name] MD, MS, PH Submitted: 2/12/2016			2 Ctudy Leastian and Cha	onsors		
		-)				
	SELF-MANAGEMENT DREN WITH CHRONIC	INTERVENTION FOR MEDICAL COMPLEXITY				
		2. Study I	ocation and Sponsors.			
	Add all locations app Protection Program (arch via the University of Uta	h IRB or	Human Re	search

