Focus Groups and Usability testing session will generate valuable input/feedback about the how the MyChild^{CMC} tool will be develop and used. We will add IRB amendments for the parent permission consent when we are ready to add participants. Because we cannot anticipate all the changes we have just added the first consent (attached) for the Focus Group.

Focus Groups: three focus groups (6-8 parent participants per session) with 24 parent participants in Year 1 and two usability testing cycles, each assessing 6 parent participants (for a total of 12 parent participants) in Year 2. Participants will receive participant remuneration equivalent to a \$50 gift card after participating in each focus group and usability testing. The PI and all members of the Research Team will adhere to all University of Utah Payments to Human Research Participants rules and regulations.

A written flyer describing the study will be displayed in Comprehensive Care Clinic at Primary Children's Hospital ([name] (Co-I) is the medical director in this clinic) to recruit potential participants. If a parent is interested in participating, a research staff will approach them to consent and enroll in the study.

Patients/Parents will be identified by the CMC study coordinator ([name], [name]) in CMC clinics or the inpatient at PCH, or those who express interest in participating in the study after seeing the written flyer posted in the clinic. The family will then be approached by the study coordinator to participate in the study if they meet criteria. The study coordinator will obtain a signed consent form from the patient/parent to participate in the study. After enrollment, patients/parents will be trained during the formal education about the MyChild^{CMC} app, the dynamic run chart report (including definitions of the scale and colors) as well as the Patient Portal. Participants will download the MyChild^{CMC} app onto their smartphones and create a log-in account. Patients will be trained in how to use the system. Patients also will be encouraged to bring the form to their primary care provider at the time of follow-up visit. A contact number will available for questions and support regarding any technical aspects of the MyChild^{CMC}.

5. How will consent be obtained?

Informed Consent Process (with or without a document)

6. Describe all the procedures chronologically, from screening/enrollment through study closeout, which will be completed in the research project.

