Validated surveys will be used to collect data, including a 37-item Caregiver Priorities and Child Health Index of Life with Disabilities (CPCHILD) Questionnaire (child QOL), 12-item Parent satisfaction questionnaire, which includes one open-ended question assessing participant's perception of burden related to MyChild^{CMC} use, 13-item Patient Activation Measure (caregiver self-management skills), 12-item Short Form health survey (caregiver QOL), and a 6-item Newest Vital Sign (NVS) for caregiver health literacy. At each QOL, we will also collect caregiving burden summary over the past month for both the intervention and control groups. All HCP caring for CMC during the study period will be surveyed at the end of the study to assess their satisfaction with care using the 6-item HCP Satisfaction Questionnaire. ED and hospital admissions will be collected using the Intermountain enterprise data warehouse (EDW),152 an integrated database linking data of 22 hospitals in Utah and Idaho. Intermountain Healthcare provides services for > 95 % of children in Utah.

7. Are all procedures for research purposes only (non-standard or non-standard of care procedures)? Yes O No

If no, list the procedures that are performed for research purposes only (non-standard or non-standard of care procedures):

8. Is there a safety monitoring plan for this study?

🔿 Yes 🌑 No

9. Provide a summary of the statistical methods, data analysis, or data interpretation planned for this study. Factors for determining the proposed sample size (e.g., power) should be stated.

Data Analysis. We will assess Feasibility, using family's participation, retention, adherence, and dropout rates. We will also assess parent responses to interactive activities such as response to reminders and alerts, to inform the future enhancement, and the appropriateness of the alerts triggered by the MyChild^{CMC} app. Preliminary Impact: The primary outcome is QOL score, obtained at baseline, 1 and 3 months. Secondary outcomes are QOL sub-domains (comfort, emotions, communication and social interaction, health, and overall QOL), ED/hospital admissions and caregiver satisfaction. Further detail will be provided during phase 2.

AIM 2

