Data Analysis: The primary outcome is the CPCHILD total score, which will summarize the child's QOL at baseline, and at 3, 6, 9 and 12 months of follow-up. Secondary outcomes include additional CPCHILD sub-domains beyond the total CPCHILD (comfort and emotions; communication and social interaction; health; and overall QOL), child ED/hospital admission, and caregiver satisfaction, self-management skills, caregiver burden, and HCP satisfaction. The primary and secondary analyses will be performed in accordance with intention-to-treat, with patients analyzed in accordance with the randomized treatment assignment irrespective of compliance. Numeric outcome variables exhibiting positive skewness may be transformed to better approximate normality. Analyses will be performed with SAS version 9.4 or higher. Standard statistics including means, standard deviations, medians, and interquartile ranges for continuous variables and frequencies and percent for categorical variables will be used to compare characteristics of randomized vs. non-randomized patients and to compare baseline characteristics between randomized groups. Open-ended questions of caregiver and HCP satisfaction will be analyzed using standard qualitative analysis as described in Aim 1.

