The primary analysis of the CPCHILD total score will be performed by applying a linear mixed effects model to compare the mean QOL score over the 3, 6, 9 and 12-month assessments between the intervention and control groups. The mixed effects model will incorporate an unstructured covariance matrix to account for serial correlation within the same patients, and will include fixed effect terms for the randomized treatment assignment, the baseline CPCHILD total score, Clinic, and the WeeFIM and age group randomization strata as well as interaction terms between each of these factors and follow-up visit. Adjustment for the baseline CPCHILD total score will account for any baseline imbalances in the outcome variable and regression to the mean, thereby increasing statistical power. In addition to the primary comparison of the mean CPCHILD total score over all 4 follow-up assessments between the randomized groups, secondary contrasts will be constructed to estimate treatment effect on the mean total score at each individual follow-up visits and to compare the size of the treatment effects between different follow-up visits to determine if the treatment effect attenuates or increases over time. Secondary outcomes will be compared between the randomized groups using similar linear mixed models for numeric outcomes (e.g., other CPCHILD subscales, caregiver/HCP satisfaction, PAM score, and burden score) or generalized linear models with use of robust empirical standard errors for categorical outcomes. Similar analysis will be used to compare caregiver burden subscales (stress and coping). The rate of ED visits and hospital admissions will be compared between randomized groups using negative binomial regression, possibly augmented to account for 0-inflation if the proportion of subjects with 0 ED events or hospitalizations exceeds that accounted for by the negative binomial model

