This study will facilitate early identification of acute deteriorations of crosscutting symptoms to facilitate timely decisionmaking in order to prevent an ED or hospital admission. We are not making any claims that participants will benefit directly from participation in this study. However, based on our preliminary studies with the electronic-AsthmaTracker showing significant reduction in ED/hospital admissions, it is likely that patient in the current study will have improved outcomes, including improved QOL and reduced ED/hospital admissions. In addition, we anticipate that parents will have improved satisfaction, self-management skills, QOL, and reduced impact of caregiving. Further, the health care provider will benefit from additional objective data to facilitate timely decision-making. Our project will provide useful information about factors critical to caregiver self-management engagement and burnout that can be addressed to facilitate broad dissemination of self-management systems or versions of them, may be adopted by clinics and health care organizations nationwide to improve care of CMC overall.

3. Are there any costs to the participants from participation in research?

🔿 Yes 🌑 No

If yes, specify:

4. Is there any compensation to the participants?

• Yes 🔿 No

a. If yes, answer the following:

Specify overall amount:

Participants in the focus group and usability testing will receive \$50 gift card for participating.

Participants enrolled to use the MyChildCMC app will be compensated in total \$120 in gift cards: \$40 for completing enrollment and baseline surveys \$40 each for 2 follow-up surveys that will be sent via RedCAP.

All participants enrolled to use the MyChildCMC app will receive a new pulse oximeter (valued at \$20) to measure their child's blood oxygen level as part of the study.

Participants randomized to MyChildCMC group will receive a stethoscope (valued at \$5) to measure their child's respiratory rate as part of the study.

b. Specify when participants will be paid (e.g. at each visit, at end of study, etc.): Participants in focus group and usability testing will receive \$50 gift card at then end of the session.

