3.	List the identifying information you plan to collect or keep a link to (e.g. names, dates, or identification numbers such as social security numbers or medical record numbers, etc). EMPI, Encounter, Admit Date, Discharge Date, Date of Birth, Age, Sex, Race, Weight, Height, PCP, Insurance Code, Composite Score, Length of Stay, Cost, Hospital/ED Readmissions
4.	Explain why the PHI to be used or disclosed is the minimum necessary to accomplish the research objectives: The PHI is a prerequisite to identifying and pulling charts for manual review, and for administrative database information retrieval. The PHI we are collecting will be used to improve our ability to provide high quality complex medical care and will provide critical information for quality improvement.
5.	Explain why the research could not practicably be conducted without the waiver of authorization. For example, complete the following sentence: "If I had to obtain authorization, the research could not be conducted because" The PHI accessed through chart review will provide Quality Improvement (QI) data as it will be given to pediatric clinical program leaders. Impacts of QI interventions on hospitalization outcomes and patient related measures targeted at reducing re-admissions have not been evaluated. By obtaining authorization, selection bias is introduced, which minimizes the generalizability of the study outcomes.
6.	Describe your plan to protect the identifiers from improper use and disclosure, and indicate where the PHI will be stored and who will have access: All investigators and project staff sign confidentiality pledges annually and receive IRB and HIPAA privacy and data security compliance training annually. All source/legacy data files regarding patient EDW data will be stored behind the Intermountain fire wall and will be accessed only by staff members working on this study.

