C.	sponsor	Has the project funding already been approved by the sponsor or funding agency? Approved			
d.	Childre	Location of Research in addition to Primary Children's (i.e., PCH Riverton, or other Intermountain facilities			
	None				

- 4. Will data be pulled from any PCH or Intermountain electronic system(s)?
 - Yes O No
- 5. Do you need a qualified data analyst from intermountain to query an Intermountain or PCH database in order to produce a limited data set for your study?
 Yes No
- 6. Will individuals associated with this study need to be granted access to PCH or Intermountain information systems?
 Yes No
- 7. Will patient consent be obtained for access to the patient information?
 Yes No

- 8. Could there be any inventions developed from this research?
 Yes No
- Does this study involve inpatients?
 Yes O No
 Check all that apply:
 Infant Medical Surgical Unit (IMSU)

Children's Medical Unit (CMU)

Pediatric Intensive Care Unit (PICU)

10. Does this study involve outpatients?

Yes No

- a. Percent Inpatient: 20
- b. Percent Outpatient: 80
- c. Check all that apply:

Other (List)

If Other, please list: Outpatient Services

- Will ANY of the participants be non-English speaking?
 Yes No
- 12. Does this study involve any other PCH departments?
- 13. Will the PI, study coordinator, research assistant or other person associated with this proposal need access to PCH facilities, systems, or equipment that they don't already have?
 Yes
 No
- 14. Will PCH staff be required to perform any duties associated with this study in addition to routine patient care activities? ○ Yes ● No
- 15. Are diagnostic studies required as part of this study? ○ Yes ● No
- Are any diagnostic studies requested above standard of care intended to be charged to an institutional account?
 Yes
 No
- 17. This study is not an investigational drug study. This study is not an investigational use of a medical device study.

Participants PCH 1st year: 24 Participants PCH total study: 300

18. Cybersecurity Questions for Intermountain

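### The secondary ED/hospital endpoint does not separate unplanned from scheduled admissions or say when counting starts; a short definition would protect its power at little cost

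*Combined protocol and SAP*

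**What the plan says.** **The endpoint.** Section 4 (Study Information), item 6, gives the source: "ED and hospital admissions will be collected using the Intermountain enterprise data warehouse (EDW". In item 9, the AIM 2 data analysis lists the outcome among the secondary ones: "child ED/hospital admission, and caregiver satisfaction, self-management skills, caregiver burden, and HCP satisfaction". The analysis sentence is "The rate of ED visits and hospital admissions will be compared between randomized groups using negative binomial regression", with a possible zero-inflated extension. None of these places mentions unplanned, acute or elective events, the start or end of counting, or a time-at-risk offset.

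**The target of the app.** The background in section 1 ties recurrent use to "frequent acute deteriorations of their health status often for potentially avoidable causes and/or technology malfunctions that lead to recurrent ED/hospital admissions". The Vulnerable Populations page also speaks of avoidable acute deteriorations. Section 6 (Risks and Benefits), item 2, gives the purpose as "early identification of acute deteriorations of crosscutting symptoms to facilitate timely decisionmaking in order to prevent an ED or hospital admission".

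**Inpatient recruitment.** Section 4, item 4, finds families "in CMC clinics or the inpatient at PCH". The Consent Process page describes identifying families during a hospital stay and training them before discharge. The hospital's own form, item 10, records "Percent Inpatient: 20". Section 4, item 6, on the other hand, places enrolment and first login in the clinic.

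**Data fields.** Item 3 of the waiver request begins "EMPI, Encounter, Admit Date, Discharge Date, Date of Birth, Age, Sex, Race, Weight, Height, PCP" and goes on to insurance code, a composite score, length of stay, cost and readmissions. Admission type is not listed.

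**The concern.** The app works through symptom monitoring and alerts to a care coordinator. Such a mechanism can plausibly avert an acute admission; it has no evident route to averting one that was already scheduled. If both kinds are counted together, the scheduled ones contribute events with a rate ratio near 1 and draw the combined ratio toward no effect.

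The missing counting start raises a smaller question of the same kind. A child randomised during a stay has an admission that treatment cannot have influenced. Whether that stay, and the days spent in it, enter the numerator or the time at risk is left to whoever builds the data set.

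At stake is the reading of Aim 2.a, where ED/hospital use is one of two named child outcomes. A null all-cause result could be taken to mean that acute deteriorations were not reduced, when the analysis had been weakened by events outside the app's reach.

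**Working it through.** **1. The plan's own figure.** The only power statement for a between-arm comparison of the whole trial concerns the CPCHILD total score: N=220, 10% loss, SD 15.4, difference 6.59, two-sided α 0.05, at least 85% power. With 1:1 allocation (assumed, as no ratio is stated), 220 × 0.90 / 2 = 99 per arm. The standard error is 15.4 × √(2/99) = 2.189, and 6.59 / 2.189 = 3.01. Power is Φ(3.01 − 1.96) = 0.853. The figure reproduces. It says nothing about ED/hospital events, for which no power is stated.

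**2. Assumed inputs.** The documents give no event rate, dispersion, planned share or target rate ratio for this endpoint. For illustration:
- control-arm mean of 4 events (all causes) per child-year, so 1 event over 3 months
- dispersion k = 0.5 for both counts
- rate ratio 0.70 for unplanned events and 1.0 for planned events
- 99 children per arm
- planned share q of control-arm events from 0 to 30%

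**3. Formulas.**
- All-cause ratio: RR_all = 1 − (1 − q)(1 − 0.70)
- Var(log RR) = [1/μ0 + k + 1/(μ0·RR) + k] / 99
- Power = Φ(|ln RR| / √Var − 1.96)

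Here μ0 is 4 for all events in a year and 4(1 − q) for unplanned events.

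**4. One case in full, q = 20%, one year.**
- All events: RR = 1 − 0.8 × 0.3 = 0.76. Var = (0.250 + 0.5 + 0.329 + 0.5)/99 = 0.01595, SE = 0.1263. |ln 0.76| = 0.2744, ratio 2.173, power Φ(0.213) = 58%.
- Unplanned events: μ0 = 3.2. Var = (0.3125 + 0.5 + 0.4464 + 0.5)/99 = 0.01777, SE = 0.1333. |ln 0.70| = 0.3567, ratio 2.676, power Φ(0.716) = 76%.

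**5. Range.**

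| Planned share | All-cause RR | 1 year: all | 1 year: unplanned | 3 months: all | 3 months: unplanned |
|---|---|---|---|---|---|
| 0% | 0.70 | 80% | 80% | 48% | 48% |
| 5% | 0.715 | 75% | 79% | 44% | 47% |
| 10% | 0.73 | 70% | 78% | 40% | 45% |
| 20% | 0.76 | 58% | 76% | 32% | 42% |
| 30% | 0.79 | 47% | 74% | 25% | 39% |

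Both windows are shown because section 4 describes 3 months of app use while the AIM 2 analysis runs to 12 months, and neither is tied to this endpoint.

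**6. Sensitivity to dispersion (one year, q = 20%).** At k = 1, power is 40% on all events against 57% on unplanned events; at k = 2, 25% against 37%. The direction does not change.

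**7. Index stays.** Suppose no planned admissions, but one index stay counted for each of 20% of children, so 0.2 per child in each arm. Over a year, RR = (2.8 + 0.2)/(4 + 0.2) = 0.714 and power falls from 80% to 76%. Over 3 months, RR = (0.7 + 0.2)/(1 + 0.2) = 0.75 and power falls from 48.3% to 38.5%. This happens only if such stays are counted.

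**8. Absolute difference.** At q = 20% it is 4 − 3.04 = 0.96 events per child-year on all events, and 3.2 − 2.24 = 0.96 on unplanned events. Only the ratio is diluted; the difference is estimated less precisely.

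**The case against.** The strongest case against is that the size rests on a quantity the documents never mention. They do not refer to scheduled admissions at all. ED visits are presumably unplanned, so only the admission part can be diluted: if half of all events were ED visits, a 20% planned share overall would require 0.20/0.50 = 40% of admissions to be elective. At 5% planned the loss is 4 points of power. This stands. It limits the size, but not the direction.

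All-cause use is also a legitimate outcome. Aim 2.a is framed simply as ED/hospital admissions, cost is among the trial's interests, and an all-cause count needs no judgement about admission type. This is a good reason to keep it as a reported result. It does not make it the sharper test of the stated mechanism.

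Three stronger readings are tempting, and the documents do not support them:
- **That dilution is established.** The endpoint is undefined rather than deliberately all-cause, and no planned share is given.
- **That acute and planned stays could not be separated later.** The waiver item asks for identifying information and is not an analysis data dictionary. It includes the encounter, and the same request provides for pulling charts for manual review. Admission type could therefore probably be recovered. Doing so after results are known would be post hoc, which is a reason to settle the rule now.
- **That index stays will be counted.** An index stay begins before randomisation, so a count by admit date after randomisation would drop it, and admit date is a listed field. The 20% on the hospital form describes the study as a whole, with a total of 300, and not specifically the randomised children. Any stay counted would fall in both arms.

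Finally, over 3 months even the unplanned endpoint has under 50% power in the illustration, so a better definition does not rescue a short window.

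**Conclusion.** The point holds as a cheap improvement to a secondary endpoint. As worded, the outcome takes in scheduled admissions on a plain reading, it does not match the acute deteriorations that the app is meant to avert, and no counting start is given although inpatients are recruited.

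The size is conditional. Under the assumptions in the working, the one-year power lost by counting all events is 4, 8, 18 and 27 points at planned shares of 5%, 10%, 20% and 30%, and nothing at zero. With the unplanned ratio at 0.70, restricting the count gave higher power at each non-zero share shown, despite fewer events. The absolute rate difference is not biased. The primary CPCHILD analysis and the sample size of 220 do not change.

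**What to change.** In section 4, item 9, AIM 2 data analysis, define the endpoint before outcome data are examined:

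- Main analysis: ED visits plus unplanned (non-elective) hospital admissions, with a visit or admit date after randomisation and a stated end of counting.
- Children enrolled as inpatients: exclude the index stay and start time at risk at discharge.
- Negative binomial model with log time at risk as offset.
- Any combined count: an ED visit that ends in admission counts once.
- Admission type: taken from the EDW, or from chart review by encounter where it is not coded. Add the field to the extract and to the waiver list if needed.
- Supporting result: all-cause ED visits and hospital admissions, analysed in the same way.

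The cost is a few sentences and one extra data field. The downsides are slightly fewer events and reliance on coded admission type. The same coding rule would apply in both arms, and the all-cause result remains visible, so a reader can see whether the restriction matters.
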